# 5.3. Final Analysis

Final analysis for the study will occur when the last subject completes the study, the data are cleaned, and the database is locked for analysis.

# 5.4. Other Analyses to Support Safety Review and Regulatory Submissions

Ongoing safety analyses for the purpose of Data Monitoring Committee (DMC) review will be conducted. Sponsor and CRO staff who work on the reporting of the study will remain blinded during Part 1. See Section 5.2 for discussion of blinding during Part 2. A CRO statistician and

CRO programmers separate from the group working on the primary analyses will be unblinded for purpose of DMC analyses.

# 6. GENERAL CONSIDERATIONS FOR DATA ANALYSES AND DATA HANDLING

# 6.1. General Summary Table and Individual Subject Data Listing Considerations

Tables and listings will be prepared in accordance with the current ICH guidelines (ICH 1995). The information and explanatory notes in the "footer" or bottom of each table and listing will include the following information:

- Date of data extraction
- Date of output generation
- Statistical Analysis System (SAS®) program name, including the path where the program is stored
- Any other output specific details that require further elaboration

Version 9.4 or higher of the SAS system will be used to analyze the data and to generate tables, figures, and listings. All SAS programs prepared to analyze the data will be properly annotated to permit uninvolved outside statistical experts to replicate all the analyses specified in this SAP.

Listings for the Part 1 interim analysis will include Part 1 treatment only. These listings will generally be sorted by subject ID, and visit, if applicable. Listings for the entire study period will include will generally be sorted by subject ID, treatment, and visit, if applicable.

Adjusted visit (as described in Table 8) will be included on listings that cover the entire study period as applicable. Listings will also include visit date, days relative to first dose of Part 1 treatment, and days relative first dose of Part 2 treatment, if applicable.

One exception to the sort order is that laboratory listings will be sorted by laboratory parameter first and then by the other variables.

For the Part 1 interim analysis, displays will be summarized by Part 1 treatment. A column that combines both active treatments will also be included (see Table 5).

Sort orderPart 1 Treatment DescriptorNotes1110 mg110 mg2150 mg150 mg3All activeCombined 110 mg and 150 mg groups4PlaceboPlacebo

 Table 5:
 Treatment Descriptors for Part 1 Only Displays
Column order will be in order of ascending dose, combined active doses, and placebo. A total column will be included as applicable. Generally, total columns are included on demographic and baseline characteristics tables as well as on certain safety tables, such as AE tables.

Demographic and baseline characteristic displays will be repeated for Part 2 to characterize the subset of subjects who continue in Part 2. Total columns will be included. For these displays the treatment descriptors will be as shown in Table 6. The descriptors shown in Table 6 also apply to any displays specific to Part 3.

Sort order	Treatment Descriptor	Notes
1	110 mg	110 mg
2	150 mg	150 mg
3	110 mg after placebo	For subjects who were originally randomized to placebo and were randomized to 110 mg for Parts 2 with continuation of treatment in Part 3.
4	150 mg after placebo	For subjects who were originally randomized to placebo and were randomized to 150 mg for Parts 2 with continuation of treatment in Part 3.

Table 6:Treatment Descriptors for Displays using only Part 2 or Part 3

For tables that cover the entire study period, 110 and 150 mg data from subjects assigned to placebo in Part 1 will be separated from 110 and 150 mg data from subjects assigned to active treatment in Part 1. For some tables, there will also be columns that combine data from each active treatment whether received in Part 2 and 3 only or during the entire study. Treatment descriptors are provided in Table 7.

Sort order	Treatment Descriptor	Notes
1	110 mg	110 mg (originally randomized)
2	110 mg after placebo	Active treatment data from subjects who were originally randomized to placebo and were randomized to 110 mg for Parts 2 and 3
3	All 110 mg	Combines 110 mg data from subjects originally assigned to placebo with 110 mg data from subjects originally assigned to 110 mg
4	150 mg	150 mg (originally randomized)
5	150 mg after placebo	Active treatment data from subjects who were originally randomized to placebo and were randomized to 150 mg for Parts 2 and 3
6	All 150 mg	Combines 150 mg data from subjects originally assigned to placebo with 150 mg data from subjects originally assigned to 150 mg
7	All active	Combines all data collected for 110 and 150 mg treatment regardless of original randomization of subject
8	Placebo	Placebo (includes data from Part 1 only)

 Table 7:
 Treatment Descriptors for Displays for Entire Study

Note: Not all columns will be required for any given table.

For tables produced by visit that combine active treatment data for those originally assigned to active treatment with those originally assigned to placebo there will be an adjusted visit that corresponds to the time since active dosing (either Day 1 for those originally assigned to active dose or Week 24 visit for those originally assigned to placebo; see Table 8). This will allow for combining data from active treatments in Part 1 (either 110 or 150 mg) with active treatment in Parts 2 and 3 that follows placebo (either 110 or 150 mg). The adjusted visit for those assigned to 110 or 150 mg in Part 1 will equal the original visit (ie, Day 1).

Original Visit	Adjusted Visit
Week 24	Day 1
Week 26	Week 2
Week 28	Week 4
Week 32	Week 8
Week 36	Week 12
Week 48	Week 24
Week 60	Week 36
Week 72	Week 48
Week 84	Week 60
Week 96	Week 72

# Table 8:Adjusted Visit for Active Treatment for Subjects Originally Assigned to
Placebo

Note: There is no visit in Part 2 that corresponds with the Week 18 visit in Part 1. Likewise, there are no Part 3 adjusted visits corresponding with original visits of Weeks 26, 28, and 32

For tables with count data, such as TEAE tables, additional displays based on the number of TEAEs per person-years of exposure may also be provided to adjust for the differing periods of exposure to active treatment for those originally randomized to placebo with those originally randomized to active treatment.

Summary tables for medications and free-text fields for HAE medication history are coded according to the World Health Organization (WHO) Drug Dictionary from March 2017. AE preferred terms (PT) and body/organ systems are coded using Medical Dictionary for Regulatory Affairs (MedDRA) version 19.1.

# 6.2. General Post Text Summary Table and Individual Subject Data Listing Format Considerations

Tables, listings, and figures will be numbered using a decimal system to indicate the main levels of unique displays and sub-levels of replicate displays. The first level represents the appendix within which the tables, figures, and listings will appear. This will be 14 for tables and figures and 16.2.x for listings. The second level of the numbering represents the type of data; 1 for study population, 2 for efficacy, 3 for safety, 4 for health outcomes, 5 for pharmacokinetics (PK), and 6 for PD. The third level of numbering represents the type of endpoint within the data type, the fourth represents a count of displays for the endpoint, and the fifth level is used for repeated tables. For example, tables may be repeated using a different population or for a subset of subjects.

Secondary titles will be used to identify the analysis population used for the displays.

In general, the listings should be sorted and presented by treatment assignment, subject number, and visit, if applicable. For Part 1 listings that include visit, visit date and study day should be

included on listings. For listings produced for the entire study that include visit, displays should include visit, adjusted visit, visit date, study day, and adjusted study day.

# 6.3. Data Management

A data management plan will be developed and approved prior to commencement of data entry. Data will be captured using the Medidata electronic data capture system. Electronic validation steps (edit checks) will be utilized, and data cleaning will occur in conjunction with each site. Prior to transfer of data provided by vendors (eg, laboratory data), a data transfer agreement including specifications for the type of file, definitions of variables, and contact information for the sending and receiving parties will be developed and finalized. The standard operating procedures (SOPs) of PharPoint, the selected statistics and programming vendor for this study, will be used.

Data will be mapped to Study Data Tabulation Model (SDTM)-compliant datasets prior to creation of Analysis Data Model (ADaM)-compliant derived datasets for use in the creation of summary tables. All analyses will be generated using SAS version 9.4 or above and in accordance with PharPoint SOPs.

# 6.4. Data Presentation Conventions

Continuous variables (eg, age) are summarized using descriptive statistics (the number of subjects with available data, the mean, SD, median, and minimum and maximum). Categorical variables (eg, race) are summarized using counts and percentages. Percentages are calculated using the total number of subjects per treatment group unless otherwise specified.

The following conventions are applied to all data presentations and summaries:

- For continuous variables, all mean and median values are formatted to 1 more decimal place than the measured value. SD values are formatted to 2 more decimal places than the measured value. Minimum and maximum values are presented with the same number of decimal places as the measured value.
- For categorical variables, the number and percentage of responses are presented in the form XX (XX.X%) where the percentage is in the parentheses.
- Date variables are formatted as DDMMMYYYY for presentation. Time is formatted in military time (24-hour clock) as HH:MM for presentation. Dates missing day are denoted as MMMYYYY and dates missing both day and month are denoted as YYYY in listings. Handling of partial dates for analysis is discussed in Section 6.8.
- Wherever possible, data will be decimal aligned.

The table of contents of statistical displays is provided in Section 17.1 as part of this SAP. Any changes to format, layout, titles, numbering, or any other minor deviation will not necessitate a revision to the SAP, nor will they be considered as deviations from planned analyses. Only true differences in the analysis methods or data handling will necessitate such documentation. The appropriate listings supporting the tables will be included and are not necessarily specified in the individual sections throughout the document.

## 6.5. Analysis Populations

### 6.5.1. Screen Failures

Subjects who give informed written consent but are not randomized to study treatment and are noted as screen failures in the electronic case report form (eCRF) are considered screen failures. Reasons for screen failure will be summarized using this population.

### 6.5.2. Safety Population

The safety population will include all subjects who receive at least 1 capsule of study treatment. This population will be used in the assessment and reporting of demographic information, BCX7353 drug concentrations, accountability, baseline disease characteristics, and safety data. Data will be analyzed according to the actual treatment received at first dose for all subjects or at first dose of Part 2 for subjects originally randomized to placebo.

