# Part 3 (48-week evaluation of safety of open-label BCX7353)

Part 3 of the study will start with the administration of the study drug dispensed at the Week 48 visit. Subjects will continue to receive the same BCX7353 dose in Part 3 to which they were randomized in Part 2 of the study in an open-label manner. Once Part 1 results are available, all subjects in Part 3 may be moved to a single dose level of BCX7353, based on the data from Part 1, if appropriate.

Study visits in Part 3 will occur during Weeks 60, 72, 84, and 96, with telephone contact at Weeks 52, 56, 64, 68, 76, 80, 88, and 92.

Subjects will continue to document all angioedema attacks that occur in a paper diary throughout Part 3 and will have regular visits to assess safety and tolerability. Investigator confirmation of attacks will not be required for Part 3. All attacks recorded by the subjects will be reviewed and confirmed or rejected according to a set of pre-defined rules prior to inclusion in effectiveness analyses. These rules, which were constructed in concert with HAE-treating physicians, will be outlined in this SAP.

A final study follow-up visit will be scheduled approximately 3 weeks following the last administration of study drug (Week 99).

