# 5. PLANNED ANALYSES

# 5.1. Interim Analyses

A blinded interim analysis for the purpose of sample size re-estimation after 50% of subjects (48 subjects) complete 24 weeks (See Section 4.3.2) may be conducted. A primary analysis is planned at the end of Part 1 when all subjects have completed Part 1 of the study.

An additional interim cut of the data may be required for purposes of regulatory filings when a total of 100 subjects have completed 48 weeks of dosing at 150 mg in either the current study or Study BCX7353-204, an open-label study of safety of 2 active doses, 110 and 150 mg. At the time of this data cut, an analysis of integrated safety data from Studies BCX7353-204 and BCX7353-302 may be performed. The integrated analysis will be the subject of a separate SAP. Additionally, summaries of attack rates over time by month and AE-QoL by visit, including all available data post Week 24, may be produced for the current study at the time of the integrated analysis.

# 5.2. Primary Efficacy Analysis at the End of Part 1

The primary efficacy analysis is planned after all subjects have completed Part 1 of the study (Part 1 analysis). Unblinding of the database will occur after database freeze for the Part 1 analysis. This analysis will include all data through the end of Part 1 (24-week assessment).

This is a double-blind study throughout both Parts 1 and 2. As such, study drug assignment for each subject will be blinded to the Investigator, site staff, study subjects, and clinical research organization (CRO) staff involved with study operations. Part 3 is open-label and will unblind the subject, Investigator, and site staff to Part 2 treatment assignment (but not Part 1 treatment) at the time that the subject transitions to Part 3 as Part 3 involves a continuation of the treatment received in Part 2.

During Part 1, Sponsor employees will also be blinded to the treatment allocation of individual subjects, with the exception of Sponsor staff responsible for managing clinical supplies.

The Sponsor and all other personnel who are blinded to study treatment will remain blinded to Part 1 treatment until after the database has been locked for the primary analysis at the end of Part 1.

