# 7.7. Prior and Concomitant Non-HAE and HAE Medications

Medication use is collected for the period from 30 days prior to Screening to study completion, except for contraceptives which are collected from 60 days prior. Medications collected in the eCRF that were received and stopped prior to the date of first dose will be considered prior medications. Medications will be considered as concomitant if the start date of the medication is

on or after the date of first intake of study drug or if the start date is prior to the first date of study drug but the medication is ongoing during the treatment period in the study. Medications taken at any time during Part 1 of the study will be considered with Part 1 treatment. Similarly, medications taken at any time during Part 2 or 3 of the study will be considered with Part 2 treatment. For example, a medication which is started during Part 1 while a subject is assigned to a Part 1 treatment of placebo will appear in the Part 1 only summary under the placebo column. If that treatment is continued into Part 2 where the subjects is assigned to a treatment of 110 mg, the medication will also be summarized in the treatment column labeled "110 mg after placebo" in the summary of concomitant medications for the entire study period.

Medication verbatim text will be coded using the WHO Drug Dictionary, March 2017. A summary by Part 1 treatment of recently discontinued medications taken within 30 days of screening but discontinued prior to dosing will be provided.

Separate summaries of concomitant medications for Part 1 only and for the entire study period will be presented using the treatment descriptors in Table 5 and Table 7, respectively. The number and percentages of subjects taking each medication will be summarized by WHO preferred name. Multiple uses of the same medication (by preferred name) will be counted once only per subject per study treatment. No inferential statistics will be provided.

HAE-related medications will be similarly summarized for Part 1 only and for the entire study period.

An attack-level summary will also be provided showing the number of attacks for which the various HAE-related medications were taken based on the subject diary and the concomitant medication form (androgens) in the eCRF.

All medication data will be listed.

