# 10.1. Adverse Event Preferred Term and System Organ Class Summary Tables

The following are Part 1 secondary endpoints and Part 2 and 3 primary endpoints:

- Number and proportion of subjects with a TEAE
- Number and proportion of subjects who discontinue due to a TEAE
- Number and proportion of subjects who experience a TESAE
- Number and proportion of subjects who experience a Grade 3 or 4 TEAE

AEs will be mapped to the MedDRA version 19.1 PT and system organ class (SOC). AEs are assessed by the Investigator as Grade 1 (mild), Grade 2 (moderate), Grade 3 (severe), or Grade 4 (life-threatening) according to Division of Microbiology and Infectious Diseases (DMID) using the November 2007 criteria. If a subject experiences multiple events that map to a single PT, the greatest severity grade according to the DMID criteria and strongest investigator assessment of relation to study medication will be assigned to the PT for the appropriate summaries. All AEs will be listed for individual subjects showing both verbatim and preferred terms.

TEAEs are defined as AEs that occurred on or after first dose of study treatment, whether in Part 1, 2 or 3, and will be assigned to the relevant treatment depending on when the TEAE began (Part 1 or Part 2 and 3 treatment). AEs occurring 30 days after the last dose for subjects who discontinue study treatment in Part 1 or up to 30 days after last dose in Part 2 or 3 will be considered as TEAEs and will be associated with Part 1, 2 or 3 respectively. Note that Investigators are not required to contact subjects after the last follow-up if it occurs prior to 30 days from last dose. All AEs that occurred prior to the initiation of study treatment or those recorded more than 30 days after the last dose of study treatment will be excluded from the tables but will be included in the listings.

Drug-related events are defined as those AEs that the Investigator believes were possibly, probably, or definitely related to the study drug.

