### 10.1.1. Summaries of Adverse Event Incidence Rates for All Subjects and Incidence Rates for Serious Adverse Events, Discontinuations due to Adverse Events, and Deaths

A brief summary of TEAEs will show, by treatment group, the number and percentage of subjects who 1) had any TEAE, 2) had any drug-related event, 3) permanently discontinued from study drug due to an TEAE, 4) had any serious adverse event (SAE), 5) had any Grade 3 or higher TEAE, 6) had any Grade 3 or higher drug-related TEAE, 7) had any TEAE leading to interruption of study drug, 8) had a drug-related SAE, or 9) had a fatal SAE.

TEAEs will be summarized by treatment group. For each SOC and PT, the number and percentage of subjects reporting an event will be calculated. In summary tables, SOCs and events within a SOC will be presented by decreasing frequency count based on the total number of events. Multiple events (by subject or SOC as appropriate) will be counted only once per subject per dose in each summary. For summaries that use severity grade, the most severe event will be selected.

The following summary tables (number and percentage of subjects) of TEAEs (by SOC and PT) will be provided by treatment group:

- Overall summary of TEAEs
- Summary of TEAEs
- Summary of drug-related TEAEs
- Summary of TEAEs by severity
- Summary of treatment-emergent Grade 3 or Grade 4 AEs
- Summary of drug-related, treatment-emergent Grade 3 or Grade 4 AEs

### 70

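### If the optional Part 3 move to a single dose is used, SAP 6.5.2 as written keeps switched subjects' later safety data under the dose they left

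*SAP*

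**What the plan says.** This point rests on the SAP for study BCX7353-302 alone. The supplied protocol is for study BCX7353-202, and the table shells are kept in a separate document.

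**The labelling rule.** Section 6.5.2 attributes safety data to the "actual treatment received at first dose for all subjects or at first dose of Part 2 for subjects originally randomized to placebo".

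**The option.** The Technical Summary Report, Section 4.1 and Section 4.4.2 all make continuation of the Part 2 dose the default in Part 3. All three then allow that, once Part 1 has been analysed, "all subjects in Part 3 may be moved to a single dose level of BCX7353".

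**Wording that assumes no change after Part 2 starts.**
- Section 10.1 says TEAEs "will be assigned to the relevant treatment depending on when the TEAE began (Part 1 or Part 2 and 3 treatment"), a bracket that treats Parts 2 and 3 as one treatment.
- Table 6 in Section 6.1 describes placebo starters as subjects who "were randomized to 110 mg for Parts 2 with continuation of treatment in Part 3".
- Neither Table 6 nor Table 7 has a column for a subject whose dose changes in Part 3.

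**Wording that points to treatment at the time.**
- The All 110 mg column of Table 7 "Combines 110 mg data from subjects originally assigned to placebo with 110 mg data from subjects originally assigned to 110 mg".
- Section 10.1.1 says multiple events "will be counted only once per subject per dose in each summary".
- Section 10.1.4 computes exposure by subject and by treatment.
- Section 10.2 computes compliance separately for every treatment a subject received.

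The splits that Sections 10.1.4 and 10.2 spell out run only from placebo to the later active dose.

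**The concern.** The SAP provides for a dose change in three places but does not carry it into the safety analysis. Followed as written, Section 6.5.2 fixes the label at the first dose, or at the first Part 2 dose for placebo starters. A TEAE or laboratory abnormality that arises after a move would then be reported under a dose the subject no longer takes. The left dose's columns would mix two doses. The retained dose's columns would omit this follow-up but would not be contaminated by it.

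TEAEs, Grade 3 or 4 events, Grade 3 or 4 laboratory abnormalities and drug rash are the Part 3 primary endpoints (Section 3.2.8). Section 10 repeats the safety displays for the entire study by treatment group. Because the wording pulls in two directions, two programmers could build different tables, or could place counts under one rule and person-time under another. The single dose would be chosen from Part 1 results, so without a stated rule the attribution could be settled after by-dose data are known.

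**Working it through.** **1. The plan's own durations.** Active from Part 1: 24 + 24 + 48 = 96 weeks. Placebo starters: 24 + 48 = 72 weeks of active drug. Both match the Technical Summary Report.

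**2. Inputs.** 40 subjects per Part 1 group (Section 4.3.1). Placebo subjects re-randomized 1:1 (Section 4.4.2), taken as 20/20. Part 3 runs from Week 48 to Week 96. Assumption: no dropout.

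**3. Size of the left dose's All column.** 40 × 96 + 20 × 72 = 3,840 + 1,440 = 5,280 subject-weeks (× 7 / 365.25 = 101.2 person-years).

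**4. Time in that column spent on the other dose.** 60 × (96 − s), where s is the switch week. The expression is linear in s, so s can be read as the mean switch week of the 60 switched subjects.
- Share of the All column: 60(96 − s) / 5,280.
- Share of the originally randomized column: (96 − s) / 96.
- Share of the after-placebo column: (96 − s) / 72.
- Share of time on the retained dose that its own All column would omit: 60(96 − s) / [5,280 + 60(96 − s)].

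| Switch week | Subject-weeks on other dose | All column | Originally randomized | After placebo | Omitted from retained dose |
|---|---|---|---|---|---|
| 48 | 2,880 | 54.5% | 50.0% | 66.7% | 35.3% |
| 60 | 2,160 | 40.9% | 37.5% | 50.0% | 29.0% |
| 72 | 1,440 | 27.3% | 25.0% | 33.3% | 21.4% |
| 84 | 720 | 13.6% | 12.5% | 16.7% | 12.0% |
| 96 | 0 | 0% | 0% | 0% | 0% |

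With 32 per group and a 16/16 split the shares are unchanged (2,304 of 4,224 is again 54.5%). With an assumed constant-hazard 20% dropout by Week 96 and a common switch week, the All column shares for Weeks 48, 60, 72 and 84 become 51.9%, 38.4%, 25.2% and 12.4%.

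**5. Which switch weeks are feasible.** Part 1 is analysed only after the last subject's Week 24 visit, and enrolment was planned at about 9 months, taken here as 39 weeks. The first-enrolled subject is then near Week 39 + 24 = 63 before results can exist. A common Week 48 switch would need enrolment plus reporting time of no more than 48 − 24 = 24 weeks.

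As an illustration, assume uniform enrolment over 39 weeks:
- **No reporting lag.** Subjects span Weeks 24 to 63. A fraction 24/39 = 0.615 have not reached Week 48 and would change on entering Part 3; the rest average Week (48 + 63)/2 = 55.5. The mean is 0.615 × 48 + 0.385 × 55.5 = 50.9, a share of about 51%.
- **12-week lag.** The mean is 12/39 × 48 + 27/39 × 61.5 = 57.3, about 44%.
- **26-week lag.** Subjects span Weeks 50 to 89, mean 69.5, about 30%.

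The lags are assumptions; the SAP gives no date for a move.

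**6. Effect on a rate.** If Section 6.5.2 governed both counts and person-time, the left dose's rate would be off by p × (R − 1), where p is the All column share and R is the retained dose's event rate divided by the left dose's. At R = 1 the bias is 0. At an assumed R = 1.5 it is 0.136 × 0.5 = 7% (Week 84) to 0.545 × 0.5 = 27% (Week 48) high.

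**The case against.** The case against is that the problem is doubly conditional. The move is optional, and Section 6.5.2 is a general population paragraph whose main job is to contrast actual with randomized treatment (Section 6.5.3). On that view the topic-specific sections govern: TEAEs by onset (10.1), exposure by subject and treatment (10.1.4), compliance by treatment received (10.2). This carries weight, and the intention may well have been on-dose attribution. But Section 6.5.2 is a stated rule. The bracket in Section 10.1 merges Parts 2 and 3, and the worked splits in 10.1.4 and 10.2 stop at placebo versus the active drug that follows. None of them settles a switch within Part 3.

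The consequences are also limited, and this stands. Safety analysis is primarily descriptive, no hypotheses are tested in Parts 2 and 3 (Section 8.1), and the Part 3 primary objective names no dose, so the All active column answers it.

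A reader might infer more than the documents support:
- **That Sections 7.7 and 5.2 are further safety-labelling rules.** The statement that "medications taken at any time during Part 2 or 3 of the study will be considered with Part 2 treatment" concerns concomitant medications, whose summary tables are listed on the ITT population. The remark that "Part 3 involves a continuation of the treatment received in Part 2" explains unblinding under the default.
- **That Part 3-only safety tables are affected through Table 6.** The display list in Section 17.1 contains none; the safety tables come in Part 1 and entire-study versions only.
- **That more than half of a column would be mislabelled.** A common Week 48 switch does not fit the planned enrolment. Section 4.3.2 mentions rapid enrolment but gives no figure.
- **That rates per 100 person-years would be biased.** They would not be if event rates are equal and counts and person-time follow the same rule.

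**Conclusion.** The point holds in conditional form and should be fixed. If the single-dose option is used and Section 6.5.2 is followed, post-move TEAEs and laboratory abnormalities in switched subjects sit under the dose they left in the by-dose columns of the entire-study safety displays. The documents do not show that the option will be used, nor that the programmers would let Section 6.5.2 override the other wording. They show only that no rule covers a switch within Part 3.

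The relabelled share of the All column is 40.9%, 27.3% or 13.6% at mean switch weeks 60, 72 or 84, with 54.5% as an upper bound, on the no-dropout assumptions above. These are shares of follow-up time, not errors in an endpoint. The effect is zero if no move is made. Part 1, every hypothesis test, the ITT attack-rate analyses and the All active column are untouched. The study 302 protocol or the table shells could contain a rule that was not available here.

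**What to change.** Reconcile Sections 6.5.2, 10.1, 10.1.4 and 10.2 and Tables 6 and 7 with the single-dose option in the Technical Summary Report and Sections 4.1 and 4.4.2. State one rule that applies only if the option is exercised:

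- Assign TEAEs by onset, laboratory data by sample date, and person-time, all to the dose being taken at that time.
- Take the switch date from the Part 3 dispensing and accountability records. Part 3 capsules come in dose-specific strengths (Section 4.2), so these records identify the dose. Part 3 diaries record no dosing (Table 4 footnotes), so the exact day may be approximate.
- Show switched subjects in a separate column, or flag them.
- State the denominator for a subject who contributes to two doses. Section 6.4 bases percentages on subjects per treatment group and does not cover this case.
- State the baseline for treatment-emergent laboratory grades after a switch. Section 6.6 resets baseline only for placebo starters.

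Leave the ITT attack-rate analyses by randomized treatment as they are.

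The cost is a short SAP amendment, one switch-date variable, a column or flag that stays empty if no move is made, and some imprecision in the switch day. It can be done before the final analysis and changes nothing for subjects or for Part 1.
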